^c Bicarbonate (where available), chloride, creatinine clearance, gamma glutamyltransferase, and magnesium testing are to be performed at baseline, on Day 1 (unless all screening laboratory clinical chemistry assessments are performed within 3 days prior to Day 1), and if clinically indicated.

^d If TSH is measured within 14 days prior to Day 1 (first infusion day), it does not need to be repeated at Day 1.

^e Free T3 or free T4 will only be measured if TSH is abnormal or if there is a clinical suspicion of an AE related to the endocrine system.

Table 9 Hematology

Absolute neutrophil count ^a	Absolute lymphocyte count ^a
Hemoglobin	Platelet count
Total white cell count	Coagulation

Note: For coagulation parameters, activated partial thromboplastin time (either as a ratio or as an absolute value in seconds) and international normalized ratio are to be assessed at baseline on Cycle 1 Day 1 and as clinically indicated.

^a Can be recorded as absolute counts or as percentages. Absolute counts will be calculated by Statistical Programming if entered as percentage. Total white cell count therefore has to be provided.

Table 10 Urinalysis

Bilirubin	Ketones
Blood	pH
Color and appearance	Protein
Glucose	Specific gravity

Note: Urinalysis should be done at baseline (screening) and then as clinically indicated.

Note: Microscopy is preferred to investigate white blood cells and the high power field should be used for red and white blood cells; dipstick can be used as well.

If a patient shows an AST or ALT $\geq 3 \times$ ULN together with total bilirubin (TBL) $\geq 2 \times$ ULN, refer to [Appendix E](#) for further instructions on cases of increases in liver biochemistry and evaluation of Hy's Law. These cases should be reported as SAEs if, after evaluation, they meet the criteria for a Hy's Law case or if any of the individual liver test parameters fulfill any of the SAE criteria.

All patients should have further chemistry profiles performed at 30 days (± 3 days), 2 months (± 1 week), and 3 months (± 1 week) after permanent discontinuation of IP (see the SoAs).

Any clinically significant abnormal laboratory values should be repeated as clinically indicated and recorded on the eCRF. Situations in which laboratory safety results should be reported as AEs are described in [Section 8.3.7](#).

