8.3.8 Hy's Law

Cases where a patient shows elevations in liver biochemistry may require further evaluation and occurrences of AST or ALT $\geq 3 \times \text{ULN}$ together with TBL $\geq 2 \times \text{ULN}$ may need to be reported as SAEs. Please refer to [Appendix E](#) for further instruction on cases of increases in liver biochemistry and evaluation of Hy's Law.

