For PHL and HL, the elevation in transaminases must precede or be coincident with (ie, on the same day) the elevation in TBL, but there is no specified time frame within which the elevations in transaminases and TBL must occur.

E 3 Identification of potential Hy's law cases

In order to identify cases of PHL it is important to perform a comprehensive review of laboratory data for any patient who meets any of the following identification criteria in isolation or in combination:

- ALT $\geq 3 \times$ ULN
- AST $\geq 3 \times$ ULN
- TBL $\geq 2 \times$ ULN

The Investigator will without delay review each new laboratory report and if the identification criteria are met will:

- Notify the AstraZeneca representative
- Determine whether the patient meets PHL criteria (see Appendix E 2 for definition) by reviewing laboratory reports from all previous visits
- Promptly enter the laboratory data into the laboratory CRF

E 4 Follow-up

E 4.1 Potential Hy's law criteria not met

If the patient does not meet PHL criteria the Investigator will:

- Inform the AstraZeneca representative that the subject has not met PHL criteria
- Perform follow-up on subsequent laboratory results according to the guidance provided in the Clinical Study Protocol (CSP).

E 4.2 Potential Hy's law criteria met

If the patient does meet PHL criteria the Investigator will:

- Determine whether PHL criteria were met at any study visit prior to starting study treatment (see Appendix [E 6](#)).
- Notify the AstraZeneca representative who will then inform the central Study Team
- Within 1 day of PHL criteria being met, the Investigator will report the case as an SAE of PHL (meeting serious criteria for “important medical event”) with causality assessment “yes/related” according to CSP process for SAE reporting
- For patients that met PHL criteria prior to starting study treatment, the Investigator is not required to submit a PHL SAE unless there is a significant change# in the patient’s condition
- The Study Physician will contact the Investigator to provide guidance, discuss, and agree on an approach for the study patients’ follow-up (including any further laboratory testing) and the continuous review of data
- Subsequent to this contact the Investigator will:
 - Monitor the patient until liver biochemistry parameters and appropriate clinical symptoms and signs return to normal or baseline levels, or as long as medically indicated
 - Complete the follow-up SAE Form as required

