 - Investigate the etiology of the event and perform diagnostic investigations as discussed with the Study Physician
 - Complete the 3 Liver eCRF Modules as information becomes available

A ‘significant’ change in the patient’s condition refers to a clinically relevant change in any of the individual liver biochemistry parameters (ALT, AST, or TBL) in isolation or in combination, or a clinically relevant change in associated symptoms. The determination of whether there has been a significant change will be at the discretion of the Investigator, this may be in consultation with the Study Physician if there is any uncertainty.

E 5 Review and assessment of potential Hy's law cases

The instructions in this section should be followed for all cases where PHL criteria are met.

As soon as possible after the biochemistry abnormality is initially detected, the Study Physician will contact the Investigator in order to review available data and agree on whether there is an alternative explanation for meeting PHL criteria other than DILI caused by the study treatment, and to ensure timely analysis and reporting to health authorities within 15 calendar days from the date PHL criteria was met. The AZ Global Clinical Lead or equivalent and Global Safety Physician will also be involved in this review together with other subject matter experts as appropriate.

According to the outcome of the review and assessment, the Investigator will follow the instructions below.

Where there is an agreed alternative explanation for the ALT or AST and TBL elevations, a determination of whether the alternative explanation is an AE will be made and subsequently whether the AE meets the criteria for a SAE:

- If the alternative explanation is **not** an AE, record the alternative explanation on the appropriate CRF
- If the alternative explanation is an SAE: update the previously submitted PHL SAE eCRF accordingly with the new information (reassessing event term; causality and seriousness criteria) following the AZ standard processes.

If it is agreed that there is **no** explanation that would explain the ALT or AST and TBL elevations other than the study treatment:

- Send updated SAE (report term ‘Hy’s Law’) according to AZ standard processes.
 - The “important medical event” serious criterion should be used if no other serious criteria apply.
 - As there is no alternative explanation for the HL case, a causality assessment of ‘related’ should be assigned.

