#### **3.2.3.1 Possibly-Related Adverse Events**

A PRAE is any TEAE with a relatedness to durvalumab of possible, or where the relatedness is missing. When the relatedness of a TEAE is missing on the electronic Case Report Form (eCRF), all efforts will be taken to ensure that the Investigator assigns his/her assessment of relatedness prior to DBL.

If relatedness of a TEAE is missing at the DBL, as given in Section 4.1.2, the TEAE will be considered as possibly related to durvalumab.

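### Protocol 8.2.1 and Appendix E 4.2 set different SAE triggers for potential Hy's Law cases, and Appendix E 5 does not always revisit the preset related causality

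*Protocol*

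**What the plan says.** Three places in the protocol deal with AST or ALT ≥3 × ULN together with total bilirubin ≥2 × ULN.

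- **Section 8.2.1** sends the reader to Appendix E "for further instructions on cases of increases in liver biochemistry and evaluation of Hy's Law". Its next sentence then gives a rule of its own: "These cases should be reported as SAEs if, after evaluation, they meet the criteria for a Hy's Law case". That sentence allows one other route, for a single liver parameter that meets an SAE criterion by itself.
- **Section 8.3.8** says that such cases "may need to be reported as SAEs" and also refers to Appendix E.
- **Appendix E 4.2** says "Within 1 day of PHL criteria being met, the Investigator will report the case as an SAE of PHL". The seriousness criterion is important medical event and the causality is preset to related. A patient who already met the criteria before treatment is exempt unless the condition changes significantly.

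Appendix E 5 then describes the review with the Study Physician. If the agreed alternative explanation is an SAE, the submitted report is updated, with event term, causality and seriousness reassessed. For an explanation that is not an "AE, record the alternative explanation on the appropriate CRF", the instruction ends there. A non-serious AE as the explanation has no bullet.

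SAP 3.2.3.1 defines the event class behind the primary endpoint: "A PRAE is any TEAE with a relatedness to durvalumab of possible, or where the relatedness is missing".

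**The concern.** The same laboratory result leads to two different reporting actions. Under the 8.2.1 sentence the SAE depends on how the evaluation turns out. Under Appendix E 4.2 it comes first and the evaluation follows. A site that acts on 8.2.1 could file the SAE late, or file none when Hy's Law is not confirmed and nothing else makes the case reportable.

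The second issue is separate and lies wholly within Appendix E. The related rating is assigned before anyone has looked for another cause, so it is provisional. E 5 tells the Investigator to revisit it in one of the three possible alternative-explanation outcomes. In the other two, a case that the review attributes to something else can stay on file as related.

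Hepatitis is a named durvalumab risk (Protocol 2.3.2.1 and 8.3.12), and the primary endpoint counts events by the Investigator's causality rating. Both issues therefore bear on safety reporting and on an input to the primary analysis.

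**Working it through.** **1. The two rules side by side, by outcome of the evaluation**

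| Outcome | 8.2.1 sentence | Appendix E 4.2 and E 5 |
|---|---|---|
| Hy's Law confirmed | SAE once evaluated | SAE within 1 day, related; then updated to Hy's Law, related |
| Other cause, itself an SAE | Liver case not an SAE by the Hy's Law route; the cause is reported | SAE within 1 day, related; then updated, causality reassessed |
| Other cause, non-serious AE | Liver case not an SAE by the Hy's Law route; the cause is reported | SAE within 1 day, related; no further instruction |
| Other cause, not an AE | Nothing by the Hy's Law route | SAE within 1 day, related; cause recorded on a CRF page, report not mentioned |
| Information delayed beyond 15 days | Not addressed | Hy's Law presumed; report updated when the review is complete |

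The rules agree on the final status only in the first row, and even there the timing differs.

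**2. Can a case go unreported under 8.2.1?** The sentence has a second route, through a single liver parameter that meets an SAE criterion. Section 8.3.7 adds that a deterioration in a mandated laboratory test is an AE if it meets an SAE criterion or is the reason for stopping treatment, and that associated signs or symptoms are reported. Outside those routes, a case with an agreed non-AE cause produces no event. E 4.2 assigns the important-medical-event criterion to the combined finding, not to one parameter, so the second route does not reproduce E 4.2.

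**3. When does a retained case reach the primary endpoint?** The protocol records causality as yes or no to a reasonable possibility (8.3.5), so I read the preset yes as the SAP's possible. By SAP 3.2.1 and 4.3 the event must also be Grade 3 or 4, start by Day 183, start no later than 90 days after discontinuation, and start before subsequent anticancer therapy. The endpoint counts patients, so the patient must have no other qualifying event. The definition of a potential Hy's Law case carries no CTCAE grade, so meeting it does not settle the grade condition.

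**4. Size per case.** First, the plan's own figure. Clopper-Pearson limits for x = 60 × 0.12 = 7.2 of n = 60 are 5.0% to 23.0%, half-width (23.0 − 5.0)/2 = 9.0, as in Protocol Table 11.

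One patient changing status shifts the proportion by 1/n:

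- overall: 1/102 = 1.0 percentage point
- standard cohort: 1/59 = 1.7 points
- palliative cohort: 1/43 = 2.3 points

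Illustration, assuming a starting count near the planning rate of 12% and one extra case that meets every condition in step 3:

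| Group | Before (exact 95% CI) | After (exact 95% CI) |
|---|---|---|
| All, n = 102 | 12, 11.8% (6.2 to 19.6) | 13, 12.7% (7.0 to 20.8) |
| Standard, n = 59 | 7, 11.9% (4.9 to 22.9) | 8, 13.6% (6.0 to 25.0) |
| Palliative, n = 43 | 5, 11.6% (3.9 to 25.1) | 6, 14.0% (5.3 to 27.9) |

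The shift is small against the width of each interval.

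**The case against.** The best defence is that 8.2.1 refers to Appendix E just before the sentence at issue, and Appendix E 1 presents itself as the process for identifying and reporting these cases. A site that follows the reference finds the 1-day rule. That makes a missed report less likely. It does not remove the conflict, because the next sentence in 8.2.1 states a different condition and nothing says which prevails.

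Several stronger readings are tempting, and the documents do not support them.

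- *Without the rapid SAE the sponsor would not know.* E 3 has the sponsor's representative notified when ALT, AST or bilirubin alone crosses its threshold. E 4.2 lists notification as a step apart from the SAE, and E 5 has the Study Physician make contact as soon as possible. SAP 4.5.4.1 also finds the cases from laboratory data and provides for narratives in the study report. These protect detection, though they do not put a missing case into the SAE or PRAE counts.
- *The lag is 1 day against 15.* The 15 calendar days in E 5 govern reporting to health authorities and the point at which Hy's Law is presumed. They are not a site SAE clock. The documents set no time for the evaluation that 8.2.1 awaits, so the lag cannot be stated.
- *Section 8.3.8 is a further contradiction.* Its conditional wording fits the exemptions in E 4.2, E 6 and E 7.
- *The related rating is locked in.* E 1 makes the Investigator responsible for reporting according to the outcome of the review. E 4.2 provides for a follow-up SAE form, 8.3.2 requires updated SAE data within 24 hours, and Appendix B 7 lists absence of another cause among the causality factors. What is missing is an explicit instruction in two branches.
- *Every case handled differently moves the primary result.* It does so only under the conditions in step 3 of the working.

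**Conclusion.** The concern holds in a limited form. The current text gives two SAE triggers for the same on-treatment liver values, and the cross-reference does not reconcile them. Late or absent SAE reporting is possible for a site that follows the 8.2.1 sentence, while sponsor notification and the laboratory summaries remain in place. Separately, E 5 leaves the provisional related rating without an explicit reassessment step when the agreed cause is not an AE or is a non-serious AE.

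The effect on the primary endpoint is conditional: 1.0, 1.7 or 2.3 points per qualifying patient (overall, standard, palliative). This assumes about 102 treated patients split 59 and 43, that the preset yes counts as possible in the SAP, and that the patient has no other Grade 3 or 4 PRAE in the window. The documents give no expected number of cases. I take it to be small, so this is mainly a matter of consistent safety reporting, worth correcting because the correction is cheap.

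**What to change.** - Reconcile the 8.2.1 sentence with Appendix E 4.2 so that one SAE trigger and one clock apply. For example, replace the sentence with a pointer to E 4.2, E 6 and E 7, which carry the requirement and its exemptions. Section 8.3.8 needs at most the same pointer.
- In Appendix E 5, extend the existing instruction to reassess event term, causality and seriousness to every branch with an agreed alternative explanation: not an AE, non-serious AE, and SAE. The causality that reaches the primary analysis is then the reviewed one.

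The cost is protocol wording, a clarification to sites, and a few follow-up entries on SAE reports already submitted. No new assessment is needed.

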8.2.2 Physical examinations

Physical examinations will be performed according to the assessment schedules (see the SoAs). Full physical examinations will include assessments of the head, eyes, ears, nose, and throat and the respiratory, cardiovascular, gastrointestinal, urogenital, musculoskeletal, neurological, dermatological, hematologic/lymphatic, and endocrine systems. Height will be measured at screening only. Targeted physical examinations are to be utilized by the Investigator on the basis of clinical observations and symptomatology. Situations in which physical examination results should be reported as AEs are described in [Section 8.3.7](#).

8.2.3 Vital signs

Vital signs (blood pressure [BP], pulse, temperature, and respiration rate) will be evaluated according to the SoAs. Body weight is also recorded at each visit along with vital signs.

First infusion

On the first infusion day, patients will be monitored and vital signs collected/recorded in eCRF prior to, during, and after infusion of IP as presented in the bulleted list below.

BP, pulse, temperature, and respiration rate will be collected from patients before, during, and after the first infusion at the following times (based on a 60-minute infusion):

- Prior to the beginning of the infusion (measured once from approximately 30 minutes before up to 0 minutes [ie, the beginning of the infusion])
- Approximately 30 minutes during the infusion (**halfway** through infusion)
- At the end of the infusion (approximately 60 minutes \pm 5 minutes)

If the infusion takes longer than 60 minutes, then BP, pulse, temperature, and respiration rate measurements should follow the principles as described above or be taken more frequently if clinically indicated. A 1-hour observation period is recommended after the first infusion of durvalumab.

Subsequent infusions

BP, pulse, and other vital signs should be measured, collected/recorded in eCRF prior to the start of the infusion. Patients should be carefully monitored and BP and other vital signs should be measured during and postinfusion as per institution standard and as clinically indicated. Any clinically significant changes in vital signs should be entered onto an unscheduled vital signs CRF page.

Situations in which vital signs results should be reported as AEs are described in Section 8.3.7. For any AEs of infusion reactions, the vital signs values should be entered into the CRF.

8.2.4 **Electrocardiograms**

Resting 12-lead ECGs will be recorded at screening and as clinically indicated throughout the study (see the SoAs). ECGs should be obtained after the patient has been in a supine position for 5 minutes and recorded while the patient remains in that position.

In case of clinically significant ECG abnormalities, including a QTcF (QT interval corrected for heart rate using Fridericia's formula) value > 470 ms, 2 additional 12-lead ECGs should be obtained over a brief period (eg, 30 minutes) to confirm the finding.

Situations in which ECG results should be reported as AEs are described in Section 8.3.7.

8.2.5 Early patient review for safety

Patients should be contacted 2 weeks (\pm 1 day) after receiving the first 3 cycles of durvalumab monotherapy (Cycle 1 Day 14 \pm 1, Cycle 2 Day 14 \pm 1, and Cycle 3 Day 14 \pm 1) of study drug(s) to ensure early identification and management of toxicities.

8.2.6 World Health Organization/Eastern Cooperative Oncology Group performance status

WHO/ECOG PS will be assessed at the times specified in the assessment schedules (see the SoAs) based on the following:

- 0 Fully active; able to carry out all usual activities without restrictions
- 1 Restricted in strenuous activity, but ambulatory and able to carry out light work or work of a sedentary nature (eg, light housework or office work)
- 2 Ambulatory and capable of self-care, but unable to carry out any work activities; up and about more than 50% of waking hours
- 3 Capable of only limited self-care; confined to bed or chair more than 50% of waking hours
- 4 Completely disabled; unable to carry out any self-care and totally confined to bed or chair
- 5 Dead

Any significant change from baseline or screening must be reported as an AE.

8.2.7 Other safety assessments

If new or worsening pulmonary symptoms (eg, dyspnea) or radiological abnormality suggestive of pneumonitis/ILD is observed, toxicity management as described in detail in the Dosing Modification and Toxicity Management Guidelines (see Section 8.4.5.1) will be applied. The results of the full diagnostic workup (including high-resolution computed tomography [HRCT], blood and sputum culture, hematological parameters, etc) will be captured in the eCRF. It is strongly recommended to perform a full diagnostic workup, to exclude alternative causes such as lymphangitic carcinomatosis, infection, allergy, cardiogenic edema, or pulmonary hemorrhage. In the presence of confirmatory HRCT scans where other causes of respiratory symptoms have been excluded, a diagnosis of pneumonitis (ILD) should be considered and the Dosing Modification and Toxicity Management Guidelines should be followed.

Pneumonitis (interstitial lung disease) investigation

The following assessments, and additional assessments if required, will be performed to enhance the investigation and diagnosis of potential cases of pneumonitis. The results of the assessment will be collected.

- Physical examination

- Signs and symptoms (cough, shortness of breath, and pyrexia, etc) including auscultation for lung field will be assessed
- SpO₂
 - Saturation of peripheral oxygen (SpO₂)
- Other items
 - When pneumonitis (ILD) is suspected during study treatment, the following markers should be measured where possible:
 - (i) ILD Markers (KL-6, SP-D) and β-D-glucan
 - (ii) Tumor markers: Particular tumor markers which are related to disease progression.
 - (iii) Additional clinical chemistry: C-reactive protein (CRP), lactate dehydrogenase (LDH)

Pulmonary function testing

At screening, pulmonary function will be assessed by measurement of forced expiratory volume.

8.3 Collection of adverse events

The Principal Investigator is responsible for ensuring that all staff involved in the study are familiar with the content of this section.

The definitions of an AE or SAE can be found in [Appendix B](#).

AEs will be reported by the patient (or, when appropriate, by a caregiver, surrogate, or the patient's legally authorized representative).

The Investigator and any designees are responsible for detecting, documenting, and recording events that meet the definition of an AE or SAE. For information on how to follow/up AEs see Section [8.3.3](#).

